### **12.1.2 Special Considerations in Assessing Response**

Low-level urinary M proteins may vary from measurement to measurement. For an increase in urinary M protein to be considered progression of disease it must be an absolute increase of at least  $200\text{ mg/day.}$

In quantitative immunoglobulin serum studies, the levels of heavy and light chain are often discrepant for technical reasons. If the discrepancy leads to equivocal response values, the heavy-chain value will be used since the heavy-chain value is usually a more reliable indicator because of its longer half-life and non-renal metabolism.

## **12.2 Lymphoma**

Response and progression of disease will be evaluated in this study using a modification of the international criteria proposed by the modified Cheson criteria with incorporation of PET/CT. [Cheson B, 2007]

**Measurable disease:** Measurable lesions are defined as those that can be accurately measured in at least one dimension (longest diameter to be recorded) as  $\geq 15$  mm with conventional techniques (PET, CT, MRI, x-ray). All tumor measurements must be recorded in millimeters (or decimal fractions of centimeters).

**Non-measurable disease:** All other lesions (or sites of disease), including small lesions (longest diameter  $< 15$  mm), are considered non-measurable disease. Bone lesions, leptomeningeal disease, ascites, pleural/pericardial effusions, lymphoma cutis/pulmonis, inflammatory breast disease, abdominal masses (not followed by CT or MRI), and cystic lesions are all non-measurable.

### **12.2.1 Extracutaneous Response Criteria**

Response criteria will be based on assessment following every 2 cycles for 6 months and then every 3 cycles thereafter. The criteria are as follows (GTD = Greatest Transverse Diameter; SPD = Sum of the Products of the Greatest Diameter):

#### **Complete Remission (CR):**

- No clinical, radiographic or diagnostic evidence of disease.
- No disease related symptoms.
- Abnormal biochemical values (e.g., LDH) clearly attributable to lymphoma must have normalized.
- Lymph nodes, nodal masses regressed to “normal” size:
- If  $>1.5$  cm before treatment regressed to  $\leq 1.5$  cm in GTD.
- If 1.1 to 1.5 cm before treatment, regressed to  $\leq 1$  cm in GTD (or  $>75\%$  in SPD).
- Spleen and all previously enlarged organs decreased in size. Spleen must not be palpable on exam
- Bone marrow free of disease on repeat aspirate and biopsy if initially positive.
- Normalization of PET scan.

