## **6.0 CRITERIA FOR SUBJECT ELIGIBILITY.**

### **6.1 Subject Inclusion Criteria**

1. Pathology confirmed lymphoma or multiple myeloma.
  - Hodgkin lymphoma is eligible for either phase and will be considered a B-cell lymphoma in the phase IIa study.
  - Phase IIa portion, subjects must have B-cell lymphoma, T-cell lymphoma, or multiple myeloma.
2. Relapse or progression after at least 1 systemic therapy.
3. Measurable disease for phase IIa portion only.

- Lymphoma (includes CTCL patients who are NED in skin): CT or PET/CT by modified Cheson criteria with incorporation of PET.
  - Multiple myeloma: Patient must have measurable disease and therefore must have at least one of the following:
    - i. Serum M-protein  $\geq 0.5\text{gm/dL}$  ( $\geq 5\text{gm/L}$ )
    - ii. Urine M-protein  $\geq 200\text{mg/24hr}$
    - iii. Serum FLC assay: involved FLC  $\geq 10\text{mg/dL}$  ( $\geq 100\text{mg/L}$ ) provided serum FLC ratio is abnormal.
  - CTCL: mSWAT  $>0$ , or absolute Sezary count  $\geq 1000\text{ cells}/\mu\text{L}$ .
4. Age  $\geq 18$  years at the time of signing the informed consent form.
  5. Able to adhere to the study visit schedule and other protocol requirements.
  6. Previous systemic anti-cancer therapy must have been discontinued at least 3 weeks prior to treatment in this study. If there is progression of disease on that therapy and all adverse effects have resolved to Grade 1 or baseline, in which case 2 weeks is acceptable.
  7. Previous radiation, hormonal therapy, and surgery must have been discontinued or completed at least 2 weeks prior to treatment in this study and adverse effects must have resolved. Lymph node or other diagnostic biopsy within 2 weeks is not considered exclusionary.
  8. Short course systemic corticosteroids for disease control, improvement of performance status or non-cancer indication (< 7 days) must have been discontinued at least 7 days prior to study treatment. Stable ongoing corticosteroid use ( $\geq 30$  days) up to an equivalent dose of 15 mg of prednisone is permissible.
  9. ECOG performance status of  $\leq 2$  at study entry (see Appendix A).
10. Laboratory test results within these ranges:
- Absolute neutrophil count  $\geq 1.0/\text{mm}^3$ .
  - Platelet count  $\geq 70\text{ K}/\mu\text{L}$ , if thrombocytopenia is due to bone marrow involvement platelet count must be  $\geq 50\text{ K}/\mu\text{L}$ .

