## 8.0 PRETREATMENT EVALUATION

### 8.1 Documentation of tests resulted and/or verification to be performed within 28 days of starting treatment.

- Record prior medications and treatments
- Record prior anti-cancer therapy
- Physical examination
- ECOG performance status
- 12 lead electrocardiogram (ECG)
- Complete metabolic panel, including magnesium and phosphorus
- Lactate dehydrogenase (LDH)
- Serum/urine protein electrophoresis (SPEP/UPEP), serum/urine immunofixation, and serum free light chain (**multiple myeloma patients only**)
- Bone marrow biopsy and aspiration (**multiple myeloma patients only**)
- PET/CT or CT Chest, Abdomen, and Pelvis (B-cell lymphoma, PTCL, CTCL with extracutaneous disease)
- Register patient with REMS® program.

- mSWAT for patient with cutaneous lymphoma.
- Sezary panel in patients with Sezary syndrome only.
  - Peripheral blood flow cytometry with immunoconjugates for CD2, CD3, CD4, CD8, CD26 and or CD7, and CD52.
- Pregnancy testing for females of childbearing potential within 10-14 days and again 24 hours prior to prescribing lenalidomide per the [Revlimid REMS® program](#).

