 Lymphoma: CT including at least the chest, abdomen and pelvis or PET/CT is required for response (systemic B and T-cell lymphoma patients only) assessment. A bone marrow will only be repeated to confirm a complete response if previously known to be involved. Cutaneous T-cell lymphoma patients will have imaging at baseline and (CTCL) will have an mSWAT (Appendix I) performed monthly for the first three cycles and then at each response assessment timepoints (end of cycle 4, 6 and thereafter at the end of every third cycle). In CTCL patients, imaging will be repeated if appropriate (patients with known nodal or visceral disease) every other cycle. Sezary panel in patients with Sezary syndrome. Cutaneous lymphoma patients without nodal or visceral disease will have imaging repeated only to confirm a complete response. After cycle 12, patients on continuous therapy may be imaged as clinically indicated, at the discretion of the treating physician. At discontinuation of therapy, end of study response assessments – including imaging – should be performed.

Serum/urine protein electrophoresis, serum/urine immunofixation, quantitative immunoglobulins, and serum free light chains are required if appropriate for (multiple myeloma patients only) response assessment. A bone marrow will only be repeated if to confirm a complete response. Patients with non-secretory myeloma will have the bone marrow assessment repeated if they have been otherwise clinically stable (i.e. without new lytic lesions, soft-tissue plasmacytomas or hypercalcemia). A skeletal survey is allowed to rule out bone lesions for evaluation of disease progression and to confirm a complete response in nonsecretory multiple myeloma. PET/CT should be performed at screening and to confirm responses in patients with soft tissue plasmacytomas.

 An additional safety assessment will be done 28 days (+/- 2 days) following the last dose of protocol therapy.

 If romidepsin is omitted on day 8 per dose reduction algorithm (Table 4) then hematologic and electrolyte assessments are not required.

Response assessment will be performed at the end of cycles 2, 4, and 6. Thereafter, response assessment will occur at the end of every third cycle (9,12,15, etc.) until disease progression or removal from study. Myeloma patients will have their disease assessed after each cycle.

 +/- 3 days

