#### **Complete Remission/unconfirmed (CRU):**

Patients meeting the above criteria for CR with the following exceptions:

- Residual node mass of  $>1.5$  cm in GTD regressed by  $>75\%$  in SPD.
- Individual nodes previously confluent regressed by  $>75\%$  in SPD
- Indeterminate bone marrow (increased number or size of lymphoid aggregates without cytologic or architectural atypia.)

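### Lymphoma CR and CRu both require a normal PET although CT alone is allowed, so a patient who never has a PET can be recorded as no better than PR and the complete response rate is understated

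*Combined protocol and SAP*

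**What the plan says.** Section 12.2.1 gives the extracutaneous CR criteria as a list. One item is "Normalization of PET scan", with nothing to limit it to patients who had a PET or whose PET was abnormal. The marrow item in the same list does carry such a limit: "Bone marrow free of disease on repeat aspirate and biopsy if initially positive".

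CRu is defined as "Patients meeting the above criteria for CR with the following exceptions". Three exceptions follow: a residual nodal mass, previously confluent nodes, and an indeterminate marrow. None concerns PET.

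The imaging rules let CT stand alone at every stage:

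- Eligibility (Section 6.1), measurable lymphoma: "CT or PET/CT by modified Cheson criteria with incorporation of PET".
- Baseline (Section 8.1): "PET/CT or CT Chest, Abdomen, and Pelvis".
- Response (Table 7 Legend, footnote 7): "CT including at least the chest, abdomen and pelvis or PET/CT is required for response".

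The one place where PET is called for to confirm response is footnote 8, for myeloma: "PET/CT should be performed at screening and to confirm responses in patients with soft tissue plasmacytomas". There is no matching rule for systemic lymphoma.

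Complete response rate is a secondary objective (Section 1.0). Section 14.0 reports it as a proportion with a confidence interval.

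**The concern.** The response criteria demand a test that the visit schedule does not. A patient can comply with every imaging rule, have all nodes return to normal size on CT, meet every other CR item, and still fail both CR and CRu because no PET exists. PR is then the best category open to that patient, who stays in the denominator of the complete response rate.

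The error runs in one direction. It lowers the complete response rate and moves the same patients into the PR rate, which is also a secondary endpoint. Part of what is reported as depth of response would then be a record of how often PET was ordered.

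**Working it through.** The plan gives no sample size, power or target for the complete response rate, so there is no figure to reproduce. The check has two parts.

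**1. Following one patient through the text.** Take a systemic lymphoma patient imaged by CT at baseline and at each assessment, with complete regression on CT and no PET at any time.

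- CR: the PET item cannot be shown to be met, so not CR.
- CRu: the CR items apply apart from three exceptions, none of them PET, so not CRu.
- PR: the nodal shrinkage, no-new-sites and organ items are met, so PR.

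By the definitions in Section 4.1, overall response pools CR/CRu, VGPR and PR, and time to response and duration of response both run from the first response of any of these kinds. Event-free survival does not use the response category. None of these endpoints changes when a CR is recorded as PR. Skin response in CTCL (Section 12.2.2) uses mSWAT and needs no PET. The primary objective concerns MTD and toxicity.

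**2. Illustrating the size.** Let p be the true CR/CRu rate and f the share of lymphoma patients who never have a PET. If CT-only follow-up is unrelated to response, then

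recorded rate = p × (1 − f).

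Inputs:

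- p = 15%: the CR/CRu rate cited for romidepsin in PTCL (19/130, Section 3.1.3.2).
- p = 7%: the complete response rate cited for lenalidomide in indolent B-cell lymphoma (Section 3.2.3.3, B-cell lymphoma).
- n = 36: 15 B-cell + 15 T-cell + 6 acute T-cell leukemia/lymphoma (Section 14.0). Any patient assessed on skin alone would reduce the number affected.
- f: not in the documents, so assumed over its whole range.

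| f (assumed) | Recorded rate, p = 7% | Recorded rate, p = 15% | Expected CR/CRu of 36, p = 15% | Chance that none is recorded, p = 15% |
|---|---|---|---|---|
| 0% | 7.0% | 15.0% | 5.4 | 0.003 |
| 25% | 5.3% | 11.3% | 4.1 | 0.014 |
| 50% | 3.5% | 7.5% | 2.7 | 0.060 |
| 75% | 1.8% | 3.8% | 1.4 | 0.253 |
| 100% | 0% | 0% | 0 | 1 |

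For example, 15% × (1 − 0.25) = 11.25% and 36 × 0.1125 = 4.05. The last column is (1 − recorded rate)^36.

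Section 14.0 also pools lymphoma with myeloma, where CR needs no PET, so the pooled shift is smaller. With that section's total of 44 patients and p = 15%, the loss at f = 25% is 36 × 0.15 × 0.25 = 1.35 patients. That is 1.35/44 = 3.1 percentage points, against 3.75 points among lymphoma patients alone.

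**The case against.** Several points on the other side have weight.

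- *PET remains available.* PET/CT is permitted at every response assessment, so a site can obtain one when CT shows complete regression. A reader might infer that CT follow-up permanently bars a patient from CR. The documents do not support that: only a patient who never has a PET is caught.
- *Normalisation implies an earlier abnormality.* The biochemical item in the CR list is worded that way, so a reviewer could treat the PET item as not applicable when no PET was done. This is a natural reading, but it is not written, whereas the marrow item and the PET-negative PR category both state their condition. It would also create a different unevenness: a CT-only patient would be CR with no metabolic test, while a patient with the same CT and residual uptake on PET would not.
- *The published criteria may settle it.* Section 12.2 says that the study uses a modification of them, so the protocol's own list governs. The source is not available here, and nothing is claimed about it.
- *Central review.* Section 16.1.2 makes responses from all sites subject to review by one committee, which could apply one reading throughout. A reader might infer that the rate will vary with each site's choice of scanner; given this control, that is speculation. What stands is that the committee has no written rule for a missing PET.
- *No comparison is planned.* A reader might infer that comparisons of CR rates across subtypes, or with cited single-agent rates, are invalidated. The plan tests neither, and Section 14.0 already notes that criteria differ by subtype. An informal comparison is distorted only so far as scan modality differs.
- *Sampling error is large.* The exact 95% interval for 5/36 is 4.7% to 29.5%, wide enough to contain the 11.3% and 7.5% in the table. True, but that interval describes chance, not a one-sided misclassification, and it does not warn the reader of one.

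**Conclusion.** The point holds within limits. Under Section 12.2.1 as written, a lymphoma patient with no PET and complete regression on CT is recorded as PR, and the secondary complete response rate is understated as a result. This is a stated rule that misclassifies a patient who complied with the protocol, not merely a missing detail.

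The size cannot be determined from the documents. At a true rate of 15%, CT-only shares of 25% to 75% give recorded rates of 11.3% to 3.8% among lymphoma patients; the effect is zero if every patient has PET. These figures assume that the PET item is read literally, that CT-only follow-up is unrelated to response, and that no CT-only patient receives a confirmatory PET. They illustrate the mechanism and are not estimates for this trial.

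The consequence is confined to the complete response rate and the split between CR and PR.

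**What to change.** Use one rule whose categories do not overlap.

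- **CR (Section 12.2.1):** where PET was performed at baseline or at the response time point, a negative PET at response is required for CR.
- **CRu (Section 12.2.1):** add that a patient with no PET who meets every other CR criterion is CRu.
- **Reporting (Section 14.0):** give PET-confirmed CR and CRu separately as well as combined, and show how many CRu patients were CT-only.
- **Response review (Section 16.1.2):** have the committee apply this rule to all sites.

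The edit should name the in-between case. A patient with a baseline PET and only CT afterwards needs a negative PET to be CR under this wording, and without one remains PR.

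Do not require the baseline modality to be kept. That could bar a CT-baseline patient from a confirmatory PET, or add PET scans for a patient who would otherwise have moved to CT.

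The cost is a wording change, and no scan becomes mandatory. The PET-confirmed CR count may look smaller than the combined figure. The combined CR/CRu figure will still include patients without metabolic confirmation; the separate counts disclose this but do not remove it.

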#### **Complete Remission/unconfirmed (CRU):**

Patients meeting the above criteria for CR with the following exceptions:

- Residual node mass of  $>1.5$  cm in GTD regressed by  $>75\%$  in SPD.
- Individual nodes previously confluent regressed by  $>75\%$  in SPD
- Indeterminate bone marrow (increased number or size of lymphoid aggregates without cytologic or architectural atypia.)

#### **Partial Remission (PR):**

- Greater than or equal to 50% decrease in SPD of the six largest dominant nodes/nodal masses.

- No increase in size of other nodes, liver or spleen.
- Splenic and hepatic nodes regressed at least 50% in SPD.
- No new sites of disease.
- Bone marrow and organs other than the spleen and liver cannot be considered for evaluation for PR because involvement at these sites is considered evaluable but not measurable.

**PET negative Partial Remission (PET- PR):**

- Patient meets above criteria for PR with resolution of previous PET positive lesions.

**Stable Disease (SD):**

- Patients who have achieved less than a partial remission but who have not developed findings consistent with progressive disease.

**Progressive Disease (PD):**

- In patients previously CR, CRu, PR or SD.
- Greater than or equal to 50% increase in SPD of any previously identified abnormal node.
- Appearance of any new lesion during or at the end of therapy

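### The extracutaneous lymphoma progression rule states no minimum size and no comparator, so one node can meet the PD rule and the CR size limit at once.

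*Combined protocol and SAP*

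**What the plan says.** Three parts of section 12.2 of the combined protocol and SAP bear on this.

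- **Progression (12.2.1, PD).** The rule applies "In patients previously CR, CRu, PR or SD". It is met by "Greater than or equal to 50% increase in SPD of any previously identified abnormal node" or by "Appearance of any new lesion during or at the end of therapy". No minimum size, minimum absolute increase, reference scan or confirmation step is given.
- **Normal size (12.2.1, CR).** Under the item "Lymph nodes, nodal masses regressed to" normal size, a node above 1.5 cm before treatment must come down to 1.5 cm or less in greatest transverse diameter (GTD). A node of 1.1 to 1.5 cm must come down to 1 cm or less, or shrink by more than 75% in SPD (the sum of the products of the greatest diameters).
- **Measurability (12.2).** Lesions are measurable from 15 mm; anything smaller is non-measurable disease. This is not linked to the PD rule.

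Section 12.2 describes its criteria as a "modification of the international criteria proposed by the modified Cheson criteria with incorporation of PET/CT", and 12.2.1 then sets out its own list. Under section 4.1, progression ends both DOR and EFS. Under section 13.1 it ends study treatment.

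**The concern.** A purely relative threshold is most easily crossed where the node is smallest and a reading error of a millimetre or two matters most. Here it is applied to nodes that the neighbouring CR item may still accept as normal in size, and to nodes too small to be measurable under 12.2.

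A false progression closes a patient's DOR and EFS too early. If it comes before a first response, it also ends treatment and removes later chances to respond, so the overall response rate (ORR) could fall. Section 14.0 plans 15 + 15 + 6 = 36 lymphoma patients among about 44 treated at the MTD. Up to that many are exposed to the rule, though not all will have small nodes and some cutaneous cases are scored under 12.2.2.

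The protocol guards against this elsewhere. Myeloma progression (12.1.1) carries absolute minimum increases and is measured from the lowest response value. Cutaneous progression (12.2.2) is measured from baseline and should be confirmed by a second assessment. Nodal lymphoma has neither a floor, a stated reference nor a confirmation.

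**Working it through.** The plan gives no figure that depends on this rule, so there is none to reproduce. The check is geometry, followed by an illustration on assumed reading error.

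**1. What a 50% rise means.** For a square node of side d, the product goes from d² to 1.5d², so each diameter grows by √1.5 = 1.2247, or about 22.5%. That is 8 to 9.8 mm (+1.8 mm), 10 to 12.25 mm (+2.25 mm), or 12 to 14.7 mm (+2.7 mm; 144 to 216 mm²).

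**2. Overlap with the CR size limits, measured from the smallest or previous size.** The largest square node that can rise 50% and stay within its limit is:

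- above 1.5 cm before treatment (limit 15 mm): 15 / 1.2247 = 12.2 mm;
- 1.1 to 1.5 cm before treatment (limit 10 mm): 10 / 1.2247 = 8.2 mm.

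Up to those sizes the same reading meets the PD rule and the CR size criterion.

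**3. The same check measured from baseline.** A 16 mm square node would need 16 × 1.2247 = 19.6 mm, well above 15 mm. For nodes above 1.5 cm before treatment the overlap largely disappears.

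**4. Small baseline nodes, any comparator.** A node of 11 x 10 mm is abnormal before treatment but below the 15 mm measurable limit. Read at 14 x 12 mm, the ratio is 168 / 110 = 1.53, so changes of 3 mm and 2 mm make PD. A new lesion counts at any size.

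**5. Illustration of false PD.** The documents give no measurement error. Assume independent normal error on each diameter at each scan, a node truly unchanged at 12 x 10 mm, one baseline reading, and three follow-up scans (ends of cycles 2, 4 and 6, Table 7 legend). PD is scored if any follow-up product is at least 1.5 times the baseline product. By simulation (repeat runs agree to about 0.1 point):

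| Assumed SD per diameter | 1 mm | 1.5 mm | 2 mm |
|---|---|---|---|
| Rule as written | 3.7% | 16% | 28% |
| Baseline reading must be at least 11 mm | 1.9% | 9.1% | 17% |
| As written, plus node must exceed 1.5 cm | 0.1% | 2.0% | 7.9% |
| Both conditions | 0.05% | 1.4% | 5.9% |

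A 25 x 20 mm node gives 0%, about 0.4% and 3.4% under the rule as written, so the risk sits in small nodes.

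For a shrunken node in a responder, compare two single readings of an unchanged 12 x 12 mm node. The false-PD chance per comparison is 0.8%, 5.6% or 12%; for a 20 mm square node it is 0.0%, 0.4% or 2.3%.

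**The case against.** The strongest reply is that the conflict is narrower than it looks. Most of that reply stands.

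- **The comparator matters.** A reader might infer that nodes the section calls normal count as PD whichever reference is used. They do not: step 3 shows that the overlap largely needs the smallest or previous size. That is the natural reading, because the rule covers patients in CR, and a baseline reference would require such a patient's node to exceed its pre-treatment size by 50%. It is still an inference, since the text names no reference.
- **The 11 x 10 mm node is never normal.** Its limit is 1 cm, not 1.5 cm, so it is abnormal at baseline and larger afterwards. It shows sensitivity to small changes, not a contradiction with the CR item.
- **Small is not disease-free.** A reader might infer that a new 8 mm lesion is below anything the section treats as disease. Section 12.2 calls small lesions non-measurable disease, so what is missing is a stated rule.
- **The rates are not estimates for this trial.** The error SDs are assumed. Requiring a baseline reading of at least 11 mm roughly halves the risk at 1 and 1.5 mm and cuts it by about 40% at 2 mm. Phase IIa also requires measurable disease, so such nodes would be secondary ones, in an unknown number of patients.
- **The endpoints are descriptive.** DOR and EFS are secondary, with no hypothesis test in section 14.0.

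The citation of a published standard does not close the gap. The section adopts a modification of it and lists its own criteria, and that list has no floor. Response committee review (16.1.2) supplies no size limit either.

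**Conclusion.** The concern holds in a limited form. The PD rule has no minimum size and no stated comparator. With the smallest or previous size as comparator it contradicts the CR size limits for nodes up to about 12.2 mm square (above 1.5 cm before treatment) or 8.2 mm square (1.1 to 1.5 cm). This part is arithmetic and needs no assumption about reading error. Under any comparator, nodes of 1.1 to 1.5 cm at baseline can reach PD on changes of 2 to 3 mm, and a new lesion of any size is PD.

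The false-PD rates, about 2% to 28% for one 12 x 10 mm node over three scans, are illustrative. They rest on assumed SDs of 1 to 2 mm, and the range includes the version that requires a baseline reading of at least 11 mm. They do not say how far DOR or EFS in this trial would shift. The effect is confined to DOR, EFS and possibly ORR in lymphoma patients. The primary MTD and toxicity endpoint is unaffected.

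**What to change.** Reconcile the measurability text in 12.2 with the CR and PD items in 12.2.1. For scoring DOR and EFS:

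1. State the comparator for the 50% rise.
2. Add one sentence: nodal growth is not scored as PD while the node still meets the normal-size limit that the CR item sets for it (1.5 cm or 1 cm, by pre-treatment size).
3. Have the sponsor state how nodes below 15 mm at baseline count. Item 2 removes the contradiction with CR but does little for a 12 x 10 mm node, whose own limit is 1 cm; the 1.5 cm floor in the table is only a comparison.
4. Have the sponsor state whether, and from what size, a new lesion counts, consistently with the PET criteria.

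The cost is a few sentences. The downside is that a true relapse in a very small node is scored somewhat later. For example, a node above 1.5 cm before treatment that shrank to 8 x 8 mm could regrow to 15 x 15 mm (225 / 64 = 3.52, or +252%) before it counted. The delay depends on the scan schedule: scans are three cycles apart after cycle 6 and as clinically indicated after cycle 12. A wait-for-the-next-scan rule for new lesions is therefore not suggested.

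This concerns endpoint scoring only. How it relates to the end of treatment at progression in 13.1 is for the sponsor to reconcile.
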